2.2.1 IMPROVE trial organizational chart

3.0 Study overview

We will conduct a randomized, double blind, placebo-controlled, feasibility study of mometasone furoate, an inhaled cortico-steroid (ICS), for 16 weeks in individuals with SCD and recurrent cough or wheezing who do not meet clinical criteria (derived specifically for individuals with SCD) for a diagnosis of asthma. Participants will be enrolled when they are pain free and have no acute respiratory symptoms. The sample size will be 45 participants, aged ≥ 15 , with 2:1 allocation of drug to placebo. Feasibility will be determined by the proportion of individuals successfully randomized who maintain good adherence and complete at least 30 pain diaries vs. the total number enrolled.

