14.4 Aim 2: Primary and Secondary Outcomes: This aim will assess changes in pulmonary inflammation and vascular injury with ICS therapy. The primary outcomes for the trial will be **change in eNO (pulmonary inflammation) and sVCAM (vascular injury)** level 8 weeks after randomization. Secondary outcomes will be change in reticulocyte index, change in FEV₁/FVC ratio (expressed as percent predicted) and change in other key biomarkers.

14.5 Data Analysis: *Preliminary analyses* - Descriptive analyses for all socio-demographic and clinical variables will be performed. Preliminary data analyses will focus on examination of the distributional characteristics of measures used in the study. In this step, decisions will be made regarding possible transformations that might be required to meet the assumptions of the statistical tests that will be employed. Baseline values for individuals in each randomization assignment will be compared using t-tests, chi-square and non-parametric tests when appropriate. For outcomes that may be used in a definitive trial, univariate analyses will be performed first followed by stratified analyses with potential confounders (variables known or suspected to have associations with the frequency of painful episodes including age, gender, genotype, baseline hemoglobin, leukocyte count, and fetal hemoglobin percent). Potential confounders with p-value less than 0.2 will be included in parsimonious models.

14.6 Primary analyses: The primary outcome, **feasibility** as well as retention/recruitment rates, attrition points and adherence will be expressed for those enrolled from the ED and the hematology clinic. Feasibility measures will be compared between those enrolled in the ED vs. clinic using χ^2 statistics. Adherence (defined as use of greater than 70% of indicated doses by dosage counter) will be compared to the previously validated MARS-A score cutoff of 4.5 with a χ^2 statistic to validate the use of MARS-A in SCD.

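### Section 14.6 rests the validation of MARS-A on a chi-square statistic, which tests association and does not measure agreement or classification accuracy

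*Combined protocol and SAP*

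**What the plan says.** Section 14.6 (Primary analyses) defines adherence as use of more than 70% of indicated doses by the dosage counter. It says this classification "will be compared to the previously validated MARS-A score cutoff of 4.5", using a chi-square statistic, and gives the purpose as "to validate the use of MARS-A in SCD".

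That is the whole plan for this analysis. The supplied text gives it no sensitivity, specificity, predictive value, percent agreement, kappa or correlation. It states no significance level, no threshold for adequate validity and no required direction of association. It does not say which side of 4.5 counts as adherent, or at which visit the comparison is made; sections 8.6.1 and 10.5 collect adherence data at weeks 8 and 16. On size, section 3.0 says "The sample size will be 45 participants".

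**The concern.** The stated purpose and the named method answer different questions. Validating a self-report against a reference asks how many adherent and how many non-adherent people it classifies correctly. The chi-square test asks whether the two classifications are independent. Rejecting independence shows only that they are related.

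Self-report can fail by over-reporting: most people say they take the drug, including many whom the counter shows do not. Such a table can give a small p-value because the few who admit non-adherence really are non-adherent. Read as the plan is written, that p-value would support calling MARS-A valid in sickle cell disease although it misses most of the non-adherence. Nothing in the plan requires the numbers that would reveal this to be reported.

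**Working it through.** **Inputs.** N = 45 (section 3.0); reference: counter above 70% (section 14.6); index measure: MARS-A at cutoff 4.5 (section 14.6). The documents give no expected 2x2 table, power or significance level for this comparison, so there is no figure of theirs to reproduce. The tables below are illustrations, not trial data. I assume a two-sided 0.05 level (chi-square above 3.84) and that a score on the high side of 4.5 means adherent.

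**Notation.** a = adherent on both; b = adherent on MARS-A only; c = adherent on the counter only; d = adherent on neither.

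- Pearson chi-square = N(ad − bc)² / [(a+b)(c+d)(a+c)(b+d)]
- Agreement Po = (a+d)/N; chance agreement Pe = [(a+b)(a+c) + (c+d)(b+d)]/N²; kappa = (Po − Pe)/(1 − Pe)
- Sensitivity = a/(a+c); specificity = d/(b+d), with Clopper-Pearson 95% intervals

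In a 2x2 table Po − Pe = 2(ad − bc)/N². Chi-square and kappa are therefore zero together. A significant chi-square says that kappa differs from zero, not that it is large.

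**Table 1, over-reporting: (a, b, c, d) = (22, 15, 0, 8).**

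- Chi-square = 45 × (22×8 − 15×0)² / (37×8×22×23) = 45 × 30,976 / 149,776 = 9.31, p = 0.002.
- The smallest expected count is 8×22/45 = 3.9, so the exact test matters: Fisher p = 0.004. With Yates correction p = 0.008.
- Sensitivity = 22/22 = 100% (95% CI 85% to 100%).
- Specificity = 8/23 = 35% (95% CI 16% to 57%). MARS-A calls 15 of the 23 counter-non-adherent participants adherent.
- Po = 30/45 = 0.667; Pe = (37×22 + 8×23)/2025 = 998/2025 = 0.493; kappa = 0.174/0.507 = 0.34.

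The result is significant under every version of the test, yet about two thirds of non-adherent people are missed.

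**Table 2, the converse: (37, 3, 4, 1).**

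- Chi-square = 45 × (37×1 − 3×4)² / (40×5×41×4) = 28,125/32,800 = 0.86, p = 0.35.
- Agreement = 38/45 = 84%.
- Pe = (40×41 + 5×4)/2025 = 0.820; kappa = (0.844 − 0.820)/0.180 = 0.14; specificity = 1/4 = 25% (95% CI 0.6% to 81%).

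A non-significant result does not imply low raw agreement. Most of the agreement here is what chance would give when nearly everyone is adherent, and only four non-adherent people are available to judge specificity. Neither fact can be read from p = 0.35.

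**Could the test be meant as McNemar's?** That compares the two marginal proportions, so it does not measure agreement either. For (5, 18, 17, 5), McNemar's statistic is (18 − 17)²/35 = 0.03, p about 0.87, with agreement of only 10/45 = 22%.

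**The case against.** The strongest reply is that this is one sentence about a secondary instrument in a small feasibility study, and that any competent analyst would look at the 2x2 table. Much of that stands.

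A reader might infer that the test could endorse MARS-A even when the two measures run in opposite directions. Arithmetically it can. The (5, 18, 17, 5) table gives chi-square 13.88, p = 0.0002 and kappa −0.56. But an inverse table would be obvious on inspection, and nothing suggests it would be reported as validation. Among all tables of 45 with smallest expected count of at least 5 and chi-square above 3.84, 2,076 of 4,116 have agreement of 60% or less, but only 18 of those have a positive association. The lowest positive case is (13, 2, 17, 13), at 26/45 = 58%. The realistic risk is a positive association with poor specificity, as in Table 1.

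A reader might also infer that a later multicentre trial would rely on a poor adherence measure. The documents do not say that MARS-A would replace the counter. Section 14.2 defines adherence by dosage counter, and under sections 8.5 and 10.3 the unblinded coordinator documents it.

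Finally, about 45 people cannot firmly validate anything. That is correct, and it favours estimates with intervals over a p-value. It also means that changing the statistic is not enough unless the claim is softened too.

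**Conclusion.** The method does not match its purpose: as written, a significant chi-square could be taken as validation while MARS-A misclassifies many participants. In Table 1, p is 0.002 (Fisher 0.004) with specificity 35% and kappa 0.34.

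This rests on invented tables, an assumed 0.05 level and an assumed direction for the cutoff. The principle that chi-square measures association and not accuracy needs none of them. The point is limited to a subsidiary analysis. It does not touch the feasibility outcome, the treatment comparisons or the sample size, and the documents do not support a claim of harm to a later trial.

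**What to change.** In section 14.6:

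1. Base the MARS-A assessment on the 2x2 table, with sensitivity and specificity of the cutoff against the counter and Cohen's kappa, each with a 95% CI, instead of the chi-square p-value. The ROC area for the continuous score is an optional addition.
2. State which side of 4.5 counts as adherent and which visit, week 8 or week 16, supplies the data.
3. Replace the aim of validating MARS-A with that of estimating its accuracy. With 23 non-adherent participants the specificity interval in Table 1 runs from 16% to 57%. Table 1 of the plan (section 8.8) expects 50 participants at week 8. That would narrow intervals by only about 5% (√(45/50) = 0.95).

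The cost is a sentence or two of text and a few lines of analysis. No data are needed beyond the MARS-A scores and counter readings that the planned comparison already uses.

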8.5 Adherence Status Check

CRF 8 – 8 Week Adherence Status check identifies if the participant has remained adherent to study guidelines (at least 70% of doses and 15 pain diaries). CRF 8 – 8 Week Adherence Status will be filled out by RC2 as this requires that the RC visualize study medication in an unblinded fashion. If at any time the participant falls below the cut-off for medication or diaries, they will be re-instructed to bring them back to compliance.

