8.7 Pain Diary Processing

Completed pain diaries will be reviewed for missing data and accuracy (missing dates, ID number) and then brought to the SCC storage facility for processing. Complete pain diary entries are constituted by completion of questions 3 and 4. Diary entries with missing answers to question 3 and 4 will be considered incomplete. Diaries will be stored securely with other CRF's.

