14.1 Data Analyses

14.2 Primary and Secondary Outcomes: The primary outcome for the study is feasibility. **Feasibility** will be determined by calculating the proportion of randomized patients who complete follow up and a minimum of 30 pain diaries (as was required in the PiSCES study)⁷³ with good adherence to the study medication vs. the number enrolled. Other findings relevant to feasibility will include retention rate (% who complete the study), points of attrition, recruitment rates (# approached vs. # enrolled) and adherence (via dosage counters - use of more than 70% of doses) as a function of recruitment site (clinic vs. ED).

14.3 Potential outcomes for a definitive multi-center trial. We will collect outcome data which will yield imprecise estimates of effect on patient-oriented vaso-occlusive, respiratory and safety outcomes. Vaso-occlusion will be measured in 5 ways 1) daily pain diaries (see exploration of potential definitive outcomes), 2) ED visits for pain; 3) hospital admissions (or observation unit stays) for pain 4) hospital admissions for ACS and 5) Health-related quality of life (change in ASCQ-Me score). While a primary clinical outcome was not specified, sample size calculation were based on detecting a difference in pain diary data (see data analysis). Respiratory outcomes will include self-reports of symptoms from the SAC survey. Safety outcomes include infections, adverse reactions, pain, avascular necrosis, stroke and intracranial hemorrhage. Data Collection and management for

aim 1: Data will be collected by the PI or RC in the manner described in 'subject identification and recruitment' above. All ED screening forms (CRF 1) will be kept in a file in a locked cabinet in the PI's office. Relevant laboratory data will be extracted from the medical record onto case report forms (see CRFs). Data will then be manually entered into database REDCap database.

Hardcopies will be maintained in a locked file cabinet in the PI's office. Identifiable data will be kept in either the REDCap database or on harcopy locked in a file cabinet in the PI's office. Hardcopy with identifiable data will never leave the PI's office. All data that is shared outside of the PI's office (i.e with statistician) will be stripped of identifiers and participants will be identified only by a unique ID number.

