14.7 Exploration of potential definitive outcomes: For the pain diary self-report measures of pain a linear mixed repeated measures model will be implemented with the SAS procedure MIXED to compare mometasone and placebo. The nesting variable will be participant ID number; main effects will be time, treatment group and interaction of time by treatment group. This will allow for variability in the number of diaries completed and variable effects of ICS over time (expected to increase with duration of treatment). For the measures of vaso-occlusion with poisson distributions (frequency of hospital visits for pain, ED visits for pain and hospital visits for acute chest syndrome), multivariable negative binomial regressions will be performed to estimate rate ratios based on treatment assignment. We expect self-report HRQL measures (change in ASCQ-Me score) to be approximately normally distributed. Pain diary data will be expressed in terms of several summary measures as described in the PiSCES project including number of days in 'crisis', number of pain days, number of days requiring opiate use and mean pain severity.⁷¹ Categorical summary measures will be compared with χ^2 statistic, continuous variables will be compared with t-tests or non-parametric tests as appropriate. Additionally, for potential patient-oriented outcomes, a series of Bayesian analyses will be performed. For normally distributed variables (i.e. ASCQ-Me pain domains) a posterior distribution will be estimated for the difference between treatment groups. This will be achieved by using a non-informative Gaussian distribution as the conjugate prior. Markov-chain monte carlo simulation will be used to obtain random samples from the posterior distributions of each treatment group such that the distribution of the difference between treatments can be estimated. The same procedure will be used for other patient-oriented outcomes. For poisson distributed outcomes (ED visits, hospital admissions) a gamma prior will be

used, for binomial outcomes we will use a beta prior. All Bayesian analyses will be performed in R. Bayesian analyses will also be used to estimate adverse events if any occur.

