- d. They answer yes to questions 12 , 14, 15 and >15 for question 13 in group 5

Investigator Approval of Eligibility: _____ Date: _____

Supplement 3: Inhaler training and adherence modules

(Affix Label Here)
 
Participant ID: _
	
Date Form Filled Out:
 
-----
 
day month year
	
Inhaled Mometasone to Promote Reduction of Vaso-occlusive Events

---	---	---

Protocol Orientation Module A

If you lose your medication

Contact study staff immediately:

[REDACTED]
[REDACTED]
[REDACTED]
[REDACTED]
[REDACTED]

Pain diaries

Pain diaries are included in your package. Try to fill out a pain diary every day. If you miss a day that's ok. You must fill out at least 30 diaries to stay in the study.

Your medicine

This package contains your medicine for this study. Take one puff of the medicine every day. The research coordinator will teach you how to use the inhaler.

(Affix Label Here) Participant ID: _____	Date Form Filled Out: - - - - - day month year	Inhaled Mometasone to Promote Reduction of Vaso-occlusive Events
--	--	--

**Protocol Orientation Module: Adapted from “BREATHE EASIER: AN
ADULT ASTHMA EDUCATION PROGRAM” and Mometasone
Package Insert**

“Breathe Easier”

Developed by the American Institutes for Research and
the Kaiser-Permanente Medical Group

National Heart, Lung, and Blood Institute

National Institutes of Health

National Asthma Education and Prevention Program

FOR ORAL INHALATION ONLY

Please read this leaflet carefully before taking this medication

This leaflet does not contain the complete information about this medication. If you have any questions about mometasone inhalation ask your health care provider or pharmacist.

IMPORTANT POINTS TO REMEMBER

- Use this medication regularly and at the same time each day, as prescribed by your health care provider. You or your child may not get the most benefit for 1 to 2 weeks or longer after starting the medication. If you or your child's symptoms do not improve in that time frame or if your condition gets worse, contact your health care provider.
- The cap is needed to use the TWISTHALER. Do not twist the mouthpiece with your hand. When the cap is removed from the TWISTHALER, the dose counter will count down by one, and show the number of doses available after this use.

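### Section 14.7 compares counts of crisis, pain and opioid days without a denominator, although completed diaries may range from under 30 to 112 per participant

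*Combined protocol and SAP*

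**What the plan says.** Section 14.7 expresses the diary data as "several summary measures as described in the PiSCES project including number of days in" crisis, "number of pain days, number of days requiring opiate use", plus mean pain severity. Only the last is an average. On testing, it says that "continuous variables will be compared with t-tests or non-parametric tests as appropriate". No denominator, offset or rule for a missing diary day is given.

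The same section begins with a linear mixed model for the pain scores and says of it: "This will allow for variability in the number of diaries completed". That sentence covers the mixed model only.

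Diary numbers are dealt with elsewhere:

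- Section 8.5 sets the week-8 check at "at least 70% of doses and 15 pain diaries" and re-instructs anyone who falls below it.
- Section 14.2 requires "a minimum of 30 pain diaries" for the feasibility outcome.
- Protocol Orientation Modules A and B ask for a daily diary, accept missed days, and add: "You must fill out at least 30 diaries to stay in the study".
- Table 1 in section 8.8 pays by bands, from fewer than 15 diaries up to 51-56. It expects 50 participants at week 8 and 45 at the end.
- Section 8.7 defines a usable entry: "Complete pain diary entries are constituted by completion of questions 3 and 4".

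**The concern.** A count of pain days is the product of how often a participant had pain and how many diaries that participant filled in. Where the second factor varies widely, a comparison of counts is partly a comparison of diary filling.

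There are two consequences. With equal completion in both arms the test stays valid, but its spread is inflated and power falls. With unequal completion the count difference is biased; the documents do not show that this will happen, but it is possible.

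Sections 14.3 and 14.7 collect these measures as candidate outcomes for a definitive trial. A useful endpoint could therefore look poor, or the SD carried into the next sample-size calculation could be too large.

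**Working it through.** **Range of completion.** 8 × 7 = 56, which is the top of Table 1's highest band, and 16 × 7 = 112 over the treatment period. Section 8.5 re-instructs rather than removes, so totals under 30 can occur. The orientation modules say otherwise, and these passages must be reconciled. If 30 were enforced, the range would be 30 to 112 and the point would remain.

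**Same count, different disease.** Pain on 30 of 30 diary days and on 30 of 112 (27%) give the same count. Conversely, at a true share of 50%, 30 diaries give 15 pain days and 112 give 56, a 3.7-fold difference from completion alone.

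**Diary numbers under Table 1.** The percentages 50/40/10 carry no label; reading them as expected shares is an assumption. With band midpoints, the mean per 8 weeks is 0.5 × 20 + 0.4 × 38 + 0.1 × 53.5 = 30.6, or about 61 over 16 weeks. With the same band in both periods the CV is 0.39, so the SD is 0.39 × 61 = 23.8.

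**Power by formula.** Inputs are 30 active and 15 placebo (45 at 2:1, section 3.0). Assumed: pain-day share 0.50 on placebo and 0.35 on active, between-person SD 0.20. With diary mean m and SD σ, share p and between-person SD s:

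Var(count) = (σ² + m²)(p² + s²) − (mp)² + m(p − p² − s²)

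- Placebo: 4287 × 0.29 − 930 + 61 × 0.21 ≈ 326, SD 18.0, mean 30.5.
- Active: 4287 × 0.1625 − 456 + 61 × 0.1875 ≈ 252, SD 15.9, mean 21.35.
- Counts: pooled SD 16.6, SE = 16.6 × √(1/30 + 1/15) = 5.26, and 9.15 / 5.26 = 1.74. Power is about 0.40.
- Days per diary: SD about 0.209, SE 0.066, and 0.15 / 0.066 = 2.27. Power is about 0.60.

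**Power by simulation.** 6,000 trials per cell; beta-distributed pain share, binomial pain days, two-sample t-test at 5%; equal completion in both arms. The three values are for between-person SD 0.15/0.20/0.25.

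| Completed diaries | Counts | Days per diary |
|---|---|---|
| Table 1 reading (CV 0.39) | 0.51/0.39/0.32 | 0.81/0.60/0.43 |
| Uniform 30-112 (CV 0.34) | 0.57/0.45/0.35 | 0.82/0.60/0.45 |
| Uniform 60-112 (CV 0.18) | 0.74/0.56/0.40 | 0.83/0.61/0.44 |
| Uniform 90-112 | 0.82/0.61/0.44 | 0.83/0.62/0.45 |
| Uniform 90-112, 10% with the first period only | 0.74/0.56/0.41 | 0.82/0.61/0.45 |

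The 10% in the last row is Table 1's 5 of 50 who are not expected at the end. Rank tests (2,000 trials per cell, Table 1 reading) gave 0.50/0.43/0.34 against 0.78/0.59/0.43.

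**No true effect, rejection rate at nominal 5%.** At a 50% share, 20% fewer diaries on active lowers the mean count by 0.2 × 61 × 0.5 = 6.1 days with no treatment effect.

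| Completion on active | Counts | Days per diary |
|---|---|---|
| Same as placebo | 5% | 4-5% |
| 10% fewer, at random | 8-10% | 4-5% |
| 20% fewer, at random | 19-28% | 4-5% |
| 10% fewer, pain-free days only | 5% | 8-17% |
| 20% fewer, pain-free days only | 5% | 21-51% |

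**The case against.** The measures are defined by reference to a cited project, which may itself use a denominator. If so, the plan has one by reference and only needs to print it. That stands as a limit: the source cannot be checked here, and the point is that these documents do not state one. Section 2.3 says the analysis plan covers missing data, but no rule for a missed diary appears in the text available.

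The first-named diary analysis already copes with varying diary numbers, and section 14.3 promises only imprecise estimates. That also stands, and keeps the point minor.

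The power losses depend on the assumptions and shrink under others:

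- With between-person SD 0.30/0.35, counts against proportions give 0.25/0.21 against 0.32/0.26 (Table 1 reading).
- With bands drawn independently in the two periods (CV 0.29), they give 0.62/0.46/0.35 against 0.81/0.59/0.43.
- For a rarer outcome such as crisis days, 15% falling to 5% with SD equal to the mean, they give 0.80 against 0.85.

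Table 1 is also a weak guide to completion, since its percentages are unlabelled. The run with 10% giving one period starts from 45, whereas Table 1 implies about 50 contributors, 5 of them with one period. These cases reduce the loss; none reverses it.

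The strongest objection is that the proportion has its own bias. If diaries are skipped mainly on pain-free days, the count is the safer measure, as the last two rows of the second table show. This is a reason to state the assumption and report both, not to leave the denominator unstated.

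**Conclusion.** The concern holds as a minor one. As written, section 14.7 compares three day counts with no denominator, while the plan's own diary rules let completion vary about fourfold or more. Under the assumed pain rates and equal completion, the cost ranges from almost nothing (everyone at 90 to 112 diaries) to a drop in power from 0.81 to 0.51 (Table 1 reading, SD 0.15). Size is affected only if completion differs by arm, which the documents do not establish. The feasibility outcome, the mixed model and mean pain severity are not touched. The pain rates, between-person SDs and completion patterns are assumptions, and the figures apply mainly to common outcomes such as pain days.

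**What to change.** In section 14.7:

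1. Define the crisis, pain and opioid measures as days divided by completed diaries, using the definition of a complete entry in section 8.7, and compare them by the tests already named. Alternatively, use an overdispersed binomial model with completed diaries as denominator, or a negative binomial model with their logarithm as offset.
2. Use the same denominator in any Bayesian version.
3. Report completed diaries by arm and by 8-week period.
4. State the assumption that a missed diary is unrelated to that day's pain, and keep the raw count as a sensitivity analysis because the proportion is biased if the assumption fails.
5. If the cited project already uses a denominator, write it out here.

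The cost is a sentence or two and a small programming change, with no new data. The one drawback is that the proportion rests on its own missing-diary assumption, which item 4 addresses.

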SCC staff ensures that clinic site staff are properly trained, that performance of the required procedures are monitored, and that deviations from the protocol or from study norms are investigated. Routine site monitoring reports, including patient recruitment, performance of follow-up visits, and protocol compliance, will be produced at regular intervals. For spirometry, the SRC's past 10 PFT results will be reviewed to ensure reproducibility of results.

- **Quality assurance procedures**

SCC staff will conduct quality assurance audits for every 5 participants enrolled in the study. In addition, quality assurance procedures and programs will be developed and implemented for laboratory determinations, for data collection, and for data entry.

- **Randomization**

SCC staff have developed and implemented an adaptive, biased coin, covariate balanced randomization algorithm. The algorithm is implemented using a windows laptop running the program 'R' which will be carried on the IMPROVE research cart.

After screening for eligibility is complete, participants will be randomized. The Randomization algorithm will balance participants based on whether or not they take hydroxyurea and by the number of ED visits for pain during the preceding year (this variable will be trichotomized: 0-5, 6-10, 11-15).

- **Data and Safety Monitoring Board (DSMB) functions and reports**

SCC staff will prepare reports for the DSMB and will respond to ad hoc queries from the DSMB. SCC staff developed the study monitoring plan, which indicates when interim monitoring of the efficacy outcomes will be performed, how adverse events will be reported, as well as the content of the DSMB reports. The DSMB reports will include tabulations and graphical presentation of administrative data (e.g., recruitment, compliance with therapy schedule, completion of follow-up procedures, and submission of data to the SCC), efficacy data (e.g., primary and secondary outcomes of the study, as required by the monitoring plan), and safety data (e.g., the occurrence of adverse events and serious adverse events).

- **Statistical analysis plan**

[figure not shown]
SCC staff developed the statistical analysis plan, which indicates, in detail, the main analysis for the primary outcome (including intention-to-treat analyses), secondary analyses, and analyses of the secondary and safety outcomes. In addition, the plan includes the frequency of DSMB reports, and how missing data will be handled.

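### The Bayesian analysis of ED visits and admissions has no dispersion term, unlike the negative binomial regression planned for the same counts, so its intervals will be too narrow to the extent that the counts are overdispersed

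*Combined protocol and SAP*

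**What the plan says.** Section 14.7 (Exploration of potential definitive outcomes) analyses the hospital-use counts twice.

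- **Frequentist.** The sentence opens "For the measures of vaso-occlusion with poisson distributions", yet the model chosen is more general: "multivariable negative binomial regressions will be performed to estimate rate ratios based on treatment assignment". No reason is given for choosing negative binomial.
- **Bayesian.** For normally distributed outcomes, "This will be achieved by using a non-informative Gaussian distribution as the conjugate prior", and simulation then supplies "random samples from the posterior distributions of each treatment group such that the distribution of the difference between treatments can be estimated". The text continues "The same procedure will be used for other patient-oriented outcomes", and for the counts: "For poisson distributed outcomes (ED visits, hospital admissions) a gamma prior will be" used. It gives no prior parameters, dispersion term, participant-level rate or credible-interval level.

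Section 2.3 (Randomization) balances on hydroxyurea use and on prior-year ED visits for pain: "this variable will be trichotomized: 0-5, 6-10, 11-15". Section 5.3.2.2 excludes anyone with more than 15 such visits. Section 3.0 sets 45 participants, 2:1, treated for 16 weeks. Section 14.3 presents these outcomes as candidates for a definitive trial and expects imprecise estimates.

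**The concern.** A conjugate gamma prior on one Poisson rate per arm treats everyone in the arm as having the same underlying visit rate. The trial's own design says otherwise: it admits people across a range of 0 to 15 visits a year and balances on bands of that variable. When personal rates differ, counts vary more than a Poisson model allows. The negative binomial regression has a parameter for this and the Bayesian model does not.

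The posteriors describe outcomes that might be carried into a multi-center trial. In a study of 45 people their main value is an honest statement of uncertainty. A reader would also see two intervals of different width for the same counts, with no stated reason for the difference and no rule for which to use.

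**Working it through.** **Inputs from the plan.** 45 participants at 2:1, so 30 and 15; 16 weeks; prior-year visits capped at 15; balancing in three bands. The plan states no figure for these outcomes, so there is nothing to reproduce. The event rate, dispersion, prior parameters and 95% level below are assumptions.

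**Step 1: the formula.** Let a participant's 16-week count have mean μ and variance μ(1 + aμ), where a is the dispersion. The true variance of an arm mean is μ(1 + aμ)/n. With a vague prior, the Poisson-gamma posterior variance is about μ/n. Under no treatment effect the ratio, 1 + aμ, is the same in both arms. Hence, under simple allocation:

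- width factor needed = √(1 + aμ)
- actual coverage of a nominal 95% interval ≈ 2Φ(1.96/√(1 + aμ)) − 1

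**Step 2: cap and balancing ignored.** The simulated column uses 30 vs 15, no effect, a Gamma(0.5, ~0) prior and the rate-ratio interval.

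| 16-week mean μ | a | 1 + aμ | Width factor | Coverage, formula | Coverage, simulated |
|---|---|---|---|---|---|
| 1.5 | 0.25 | 1.375 | 1.17 | 90.5% | 90% |
| 1.5 | 0.5 | 1.75 | 1.32 | 86% | 86% |
| 1.5 | 1 | 2.5 | 1.58 | 78.5% | 78% |
| 3 | 0.25 | 1.75 | 1.32 | 86% | 87% |
| 3 | 0.5 | 2.5 | 1.58 | 78.5% | 79% |
| 3 | 1 | 4 | 2.00 | 67% | 67% |

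Repeated runs differ by a point or two, giving about 67-91% overall. At a = 0, simulated coverage is 95%, so the shortfall comes from overdispersion and not from the prior.

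**Step 3: do these settings fit eligibility?** A mean of 3 per 16 weeks is 3 × 52/16 = 9.75 per year. On a 0-15 range, the largest possible variance at that mean is 9.75 × (15 − 9.75) = 51. Negative binomial variance is 9.75 + 0.5 × 9.75² = 57 at a = 0.5, and 9.75 + 9.75² = 105 at a = 1. If on-trial visits resemble prior-year visits, those two rows cannot occur under the cap.

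**Step 4: cap and balancing applied.** Each participant's prior-year count is drawn from the same personal rate as the on-trial count, anyone above 15 is excluded, and allocation is near-exactly balanced on the three bands.

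- Stable personal rates: the six settings give about 90-93%, with single runs as low as 89%.
- Rates also varying within person over time (a multiplicative gamma factor with assumed dispersion 0.5): about 74-82%.

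A separate set of runs used the rate difference, annual means of 2 to 6 visits and a = 0.5 to 1. With balancing it gave 88-90% and a needed width factor of 1.15-1.21. Adding within-person variation gave 77-82%.

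**Step 5: the mild end.** The variance of an even spread over 0 to k is ((k + 1)² − 1)/12.

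- Over 0-5: mean 2.5, variance 35/12 = 2.92, a = (2.92 − 2.5)/2.5² = 0.067. The 16-week mean is 2.5 × 16/52 = 0.77, and the factor is √(1 + 0.067 × 0.77) = 1.03.
- Over 0-15: mean 7.5, variance 255/12 = 21.25, a = (21.25 − 7.5)/7.5² = 0.24. The 16-week mean is 2.31, and the factor is √1.56 = 1.25 before any benefit from balancing.

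**The case against.** The strongest reply has four parts.

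1. **The model is inferred.** Conjugacy is stated for the Gaussian case and reaches the counts only through the sentence extending the procedure. A gamma distribution on participant-level rates would itself be a negative binomial model. This stands as a limit on certainty. Even so, posteriors taken per treatment group point to arm-level rates, and if participant-level rates were meant the plan should say so.
2. **The design limits the damage.** Balancing on prior visits removes much of the chance imbalance that causes undercoverage. This stands and is the main reason for moderation. It does not remove the shortfall, and the planned biased coin would balance less exactly than the simulation did.
3. **Other analyses cover it.** The negative binomial regression is planned alongside, and section 14.5 looks at distributions first. The regression does give a sound interval, but it does not correct the Bayesian one. The decisions named in 14.5 concern transformations, not a change of likelihood.
4. **Little depends on it.** Feasibility is the primary outcome, and no decision rule uses these posteriors. This stands and lowers the severity.

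A reader might also infer that the section recognises overdispersion in one analysis and then disregards it in the other. The documents do not support that: they never mention overdispersion, and they call the counts Poisson even when choosing negative binomial.

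**Conclusion.** The two variance models for the same counts are inconsistent, and the direction of the error is known: any overdispersion that is not modelled narrows the posterior intervals. Some overdispersion is likely given the range of prior-year visits admitted.

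The best-supported size is modest. Coverage is about 90-93% for a nominal 95% interval with the cap and band balancing applied and personal rates stable. It falls to about 74-82% only on the further assumption of within-person variation, and the shortfall is near zero if participants are alike.

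A reader might infer that the intervals are certain to be badly wrong, with coverage of 67-80%. The documents do not support that. Such figures under stable rates leave out the cap and the balancing, the lowest come from settings that do not fit the cap, and the plan supplies no dispersion value.

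All figures rest on assumed means, dispersion, a vague prior, a 95% level and the arm-level reading of the model. Severity is minor to moderate: the outcomes are exploratory, but their uncertainty is what a definitive trial would draw on.

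**What to change.** In section 14.7, replace the Poisson likelihood in the Bayesian count models with a negative binomial one (Poisson with a participant-level gamma effect). State the prior on the rates and on the dispersion, and include log follow-up time as an offset. This matches the variance model of the planned regression. State the credible-interval level, and add a posterior predictive check of the variance-to-mean ratio.

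Adjusting for the two balancing factors, hydroxyurea and prior-year visit band, is a useful addition because it uses what the randomization balanced. It is not the remedy for overdispersion.

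The cost is a few more lines of R, since Markov chain Monte Carlo in R is already planned, and slightly wider intervals. No new data are needed. With 45 people the dispersion will be poorly estimated, so its prior should be reported with the results.
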